7.2. Screening

Screening Visit, Day -30 to Day 1: Clinic Visit, Pregnant Women (Visit 00 or V00)

Potential subjects will be screened for eligibility within 30 days prior to the administration of the study vaccination. The following activities will be performed:

- If not performed at the time of recruitment, subjects will be provided with a description of the study (purpose and study procedures) and asked to read and sign the informed consent form. The informed consent form will be signed prior to performing any study procedures, including any screening procedures.
- Eligibility criteria will be reviewed with prospective subjects.
- Complete medical history, including vaccination history, will be obtained by chart review and supplemented by interview of the subject to evaluate for eligibility.
- All concomitant medications and vaccinations, as determined by chart review and subject interview, taken within 90 days prior to signing the informed consent form, will be

reviewed with subjects. Medications/vaccinations reported in the eCRF are limited to those taken within 30 days prior to study vaccination.

- Obtain vital signs (oral temperature, pulse, blood pressure), height, and weight. Subjects will be asked not to eat or drink anything hot or cold, or smoke within 10 minutes prior to taking an oral temperature.
- A targeted physical examination may be performed by a study clinician licensed to make medical diagnoses and listed on the Form FDA 1572 as the site principal investigator or sub-investigator, if indicated based on review of complete medical history. For pregnant women, an examination performed by her own obstetrical clinician may also provide data when a targeted exam is called for.
- An ultrasound will be performed to date the pregnancy.
- Subjects will be given a research identification card that includes a photograph.

7.3. Enrollment/Baseline

Enrollment and Vaccination Visit, Day 1: Clinic Visit, Pregnant Women (Visit 01 or V01)

- Reconfirm subject's willingness to participate prior to performing any study procedures, including administration of the study vaccination.
- Obtain informed consent (if screening and enrollment visits have been combined).
- Review eligibility criteria with subjects prior to the study vaccination to ensure eligibility.
- Complete medical history and any updates obtained by interview and/or review of medical charts of subjects since the screening visit will be reviewed with subjects prior to the study vaccination to ensure eligibility.
- All concomitant medications and vaccinations will be reviewed with subjects prior to the study vaccination for accuracy and completeness. Any new concomitant medications/vaccinations taken since the screening visit will be reviewed with subjects and used in the assessment for eligibility, prior to the study vaccination. Medications reported in the eCRF are limited to those taken within 30 days prior to the study vaccination. Subjects will be reminded they should not plan to receive any live or inactivated vaccine within 30 or 14 days, respectively, after study vaccination.
- Vital signs, namely oral temperature, pulse, and blood pressure, will be obtained prior to the study vaccination. Vital signs assessed on Day 1 prior to the study vaccination will be considered as baseline. Subjects will be asked not to eat or drink anything hot or cold, or smoke within 10 minutes prior to taking an oral temperature.

- Height and weight will be obtained, if not done on screening visit.
- A targeted physical examination may be performed prior to the study vaccination by a study clinician licensed to make medical diagnoses and listed on the Form FDA 1572 as the site principal investigator or sub-investigator, if indicated based on review of complete medical history and any updates obtained by interview of subjects or medical chart review since the screening visit. For pregnant women, an examination performed by her own obstetrical clinician may also provide data when a targeted exam is called for.
- Approximately 30 mL of venous blood will be collected immediately prior to the study vaccination for baseline serology and cytokine assays.
- Subjects will be enrolled in Advantage eClinical and assigned to treatment arm (BOOSTRIX or Td) and post-partum study schedule.
- Pre-administration solicited event assessments will be performed prior to study vaccination to establish baseline. Subjects will then receive a single dose of study vaccine via IM injection into the deltoid muscle of the subject preferred arm. The site of injection (right or left arm) and time of administration will be recorded on the appropriate data collection form. Subjects will be observed in the clinic for at least 30 minutes after the study vaccination. The study vaccination site will be examined, post-administration solicited event assessments will be performed, and any AE/SAEs will be assessed and recorded on the appropriate data collection form prior to discharge from the clinic.
- Subjects' home addresses will be recorded so study personnel may complete follow-up home visits.
- Subjects will be instructed to notify the study center if they develop any severe reactions after the study vaccination. If the site principal investigator or appropriate sub-investigator deems the reaction severe enough, s/he will give further instructions on the proper course of action, including a return to the clinic for immediate evaluation if appropriate.
- It is possible the screening and enrollment visits may occur at the same time.

7.4. Follow-up

Follow-up visits are scheduled in reference to the study vaccination date (Day 1) as indicated for each visit window. The types of follow-up visits are described below as home visits, and clinic visits. See [Appendix A](#) for specific study visits/days and study procedures and evaluations to be conducted at each follow-up visit. At any time during the follow-up period of pregnant women, study personnel may review her medical chart to gather information about the current pregnancy that is relevant to the conduct of this study. If a woman experiences a stillbirth, all specimen

collection will stop, however the mother will be followed for safety until 6 months after the stillbirth.

7.4.1. Clinic or Home Visits

These visits will occur in person at the clinic or may be conducted by trained field officers at the participants' homes.

7.4.1.1. Post Study Vaccination Follow-up Visit, Day 4 (± 1 d): Home Visit, Pregnant Women (Visit 02 or V02)

- This visit will take place in the clinic or alternatively by trained field workers (FWs).
- Study personnel will obtain interim medical history, including an assessment for new medical conditions by interview of subjects and note any changes since the previous visit.
- Study personnel will review solicited AEs with subjects and assess and record all solicited data, AE/SAEs, unsolicited AEs, and concomitant medications/vaccinations on the appropriate data collection forms. FWs will be trained on the assessment of local and systemic reactogenicity. If the subject reports an AE that is either not included among the solicited AEs or is a grade 3 solicited AE, then the FW will contact a study clinician. The study clinician will either visit the participant at home or the participant will be referred to the study health center based on the FW's assessment.

7.4.1.2. Post Study Vaccination Follow-up Visit, Day 8 ($+3$ d): Home Visit, Pregnant Women (Visit 03 or V03)

- This visit will take place in the clinic or alternatively by trained FWs.
- Study personnel will obtain interim medical history, including an assessment for new medical conditions, by interview of subjects and note any changes since the previous visit.
- Study personnel will review solicited AEs with subjects and assess and record all solicited data, AE/SAEs, unsolicited AEs, and concomitant medications/vaccinations on the appropriate data collection forms. FWs will be trained on the assessment of local and systemic reactogenicity. If the subject reports an AE that is either not included among the solicited AEs or is a grade 3 solicited AE, then the FW will contact a study clinician. The study clinician will either visit the participant at home or the participant will be referred to the study health center based on the FW's assessment.

7.4.2. Clinic Visits

7.4.2.1. Immunology and Safety Follow-up Visit, 30 Days Post Study Vaccination Visit, Day 31 (± 4 d): Clinic Visit, Pregnant Women (Visit 04 or V04)

- Study personnel will reconfirm subject's willingness to participate prior to performing any study procedures. They will also obtain an interim medical history, including an assessment for new medical conditions by interview of subjects and note any changes since the previous clinic visit, home visit, or phone call. Study personnel will confirm that all eligibility criteria continue to be met.
- Study personnel will review the solicited AEs with subjects, if not already reviewed and recorded during previous visits, and assess and record all new AE/unsolicited AEs/SAEs and concomitant medications/vaccinations on the appropriate data collection forms.
- Vital signs, namely oral temperature, pulse, and blood pressure will be obtained. Subjects will be asked not to eat or drink anything hot or cold, or smoke within 10 minutes prior to taking an oral temperature.
- A targeted physical examination may be performed by a study clinician licensed to make medical diagnoses and listed on the Form FDA 1572 as the site principal investigator or sub-investigator, if indicated based on review of interim medical history. An examination performed by subject's own obstetrical clinician may also provide data when a targeted exam is called for.
- The study vaccination site will be examined.
- Approximately 30 mL of venous blood will be collected for post-vaccination serology and cytokine assays.

7.4.2.2. Subsequent Follow-up Visits

7.4.2.2.1. Labor and Delivery Visit, Birth (+3 d): Clinic Visit, Pregnant Women and Infants (Visit 05 or V05)

- Obtain interim medical history, including an assessment for new medical conditions by interview of subjects and note any changes since the previous clinic visit. Study personnel will solicit and record all new SAEs (as well as AEs (solicited and unsolicited)) and concomitant medications/vaccinations if less than 30 days post vaccination) on the appropriate data collection form.
- Vital signs, namely oral temperature, pulse, and blood pressure, will be obtained. Subjects will be asked not to eat or drink anything hot or cold, or smoke within 10 minutes prior to taking an oral temperature. Vital signs recorded for the mother as part of

her delivery record may be used in lieu of study personnel performing vital sign measurements.

- A targeted physical examination may be performed by a study clinician licensed to make medical diagnoses and listed on the Form FDA 1572 as the site principal investigator or sub-investigator, if indicated based on review of interim medical history. An examination performed by the subject's own obstetrical clinician may also provide data when a targeted exam is called for.
- On admission for parturition, 30 mL of blood will be drawn from the pregnant woman for serology. When possible, this blood will be drawn at the time of admission labs.
- After delivery, study personnel will review the study procedures required for the infant going forward, add the infant's name to the informed consent form, and ask the woman to acknowledge her infant's participation as well as her continuing participation by signing and dating the form again.
- If possible, 20-30 mL of cord blood will be collected at the time of delivery. If cord blood cannot be obtained, 2-5 mL of peripheral blood will be collected by venipuncture within 72 hours of birth, before discharge, when possible. Cord blood is preferred over venipuncture.
- Study personnel will record birth outcomes on the appropriate data collection form.
- Colostrum or breast milk, 10-20 mL, will be collected from the mother for serology. In Mali, women are often discharged on the same day as delivery and lactation is not always established. Thus, the first collection may occur on any of the first 4 days of life of the infant.
- The newborn infant will be enrolled into the study at the time of birth. A targeted physical examination may be performed by a study clinician licensed to make medical diagnoses and listed on the Form FDA 1572 as the site principal investigator or sub-investigator, if indicated based on review of interim medical history. A physical exam performed by the infant's doctor may also provide information, if required, for documentation.
- Axillary temperature, heart rate, respiratory rate, head circumference, length, and weight will be collected from the medical chart of the infant. If not performed as part of routine care, these measurements, except weight may be taken by qualified members of the research team within 7 days of life. Weights will only be recorded when obtained at birth.
- For infants, study personnel will solicit and record on the appropriate data collection form infant AEs, SAEs, and concomitant medications/vaccinations until the day of life 180

visit. Only medically attended AEs will be recorded. Events associated with routine newborn care and health maintenance visits will not be recorded.

- To collect cord blood and to perform physical examination of the mother and newborn at delivery, an on-call team comprised of a study physician and nurse will be posted at the recruitment site close to the delivery room. This team will collaborate with the local on-call team. The team will refer to the study ID or consent form to confirm the identification of the participant.

7.4.2.2.2. 6 Weeks Postpartum Safety Follow-up Visit, Birth + Day 42 (± 5 d): Clinic Visit, Postpartum Women and Infants (Visit 06 or V06)

- Obtain interim medical history of mother and infant, including an assessment for new medical conditions by interview of subjects and note any changes since the previous clinic visit. Study personnel will solicit and record all new congenital anomalies and SAEs on the appropriate data collection form.
- Study personnel will record infant concomitant medications on the appropriate data collection form.
- A targeted physical examination may be performed by a study clinician licensed to make medical diagnoses and listed on the Form FDA 1572 as the site principal investigator or sub-investigator, if indicated based on review of interim medical history. A targeted physical exam may be performed on the mother, infant, or both.
- 5 mL of infant venous blood will be collected for serology and cytokine assessments.
- 10-20 mL breast milk will be collected from the mother for antibody measurements.
- Study personnel will collect infant length, weight, and head circumference as well as birth outcomes on the appropriate data collection form.

7.4.2.2.3. 10 or 18 Weeks Postpartum Safety Follow-up Visit, Birth + Day 70 (± 5 d) or Birth + Day 130 (± 5 d): Clinic Visit, Postpartum Women and Infants (Visit 07 or V07)

- Obtain interim medical history of mother and infant, including an assessment for new medical conditions by interview of subjects and note any changes since the previous clinic visit. Study personnel will solicit and record all new congenital anomalies and SAEs on the appropriate data collection form.
- Study personnel will record infant concomitant medications on the appropriate data collection form.

- A targeted physical examination may be performed by a study clinician licensed to make medical diagnoses and listed on the Form FDA 1572 as the site principal investigator or sub-investigator, if indicated based on review of interim medical history. A targeted physical exam may be performed on the mother, infant, or both.
- 5 mL of infant venous blood will be collected for serology and cytokine assessments prior to receipt of DTwP.
- 10-20 mL breast milk will be collected from the mother for antibody measurements.
- Study personnel will collect infant length, weight, and head circumference as well as birth outcomes on the appropriate data collection form.

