6.3. Modification of Study Intervention/Investigational Product for a Subject

There will be no dose modifications. All subjects will receive a single 0.5 mL dose of BOOSTRIX or Td control vaccine. For pregnant women, the dose will be administered between 14 0/7 weeks gestation and 26 6/7 weeks gestation.

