6.6. Concomitant Medications/Treatments

Subject receipt of any medications, therapies, or vaccines will be recorded on the appropriate data collection form. Concomitant medications will include all current medications and medications taken within the 90 days prior to signing the informed consent form until discharge after delivery for pregnant women. For infants, concomitant medications will be recorded from birth until the day of life 180 visit.

Medications/vaccinations reported in the eCRF are limited to those taken within 30 days prior to study vaccination through discharge after delivery for pregnant women and the day of life 180 visit for infants. Participants cannot plan to receive a live vaccine within 30 days following study vaccination, nor should they plan to receive an inactivated vaccine within 14 days following study vaccination. Prescription medications, vaccinations, over-the-counter drugs, herbals, vitamins, and supplements will be recorded. Use of any new post-study vaccination medication that is not considered standard of care for conditions associated with pregnancy should prompt evaluation for the presence of a new diagnosis or condition.

Medications that might interfere with the evaluation of the investigational product should be avoided unless necessary. Medications in this category include the prohibited medications per the Subject Exclusion Criteria (see [Section 5.2](#)). In addition, the site principal investigator or sub-investigator may identify other medications that should not be used due to a risk to subject safety or assessment of reactogenicity and immunogenicity.

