^{oo}Prior to study procedures. In Mali, a research ID card with photo may be given to subjects.

[&]Venous blood for infant within 72 hrs. of birth only if no cord blood obtained.

^{ml}If not obtained in previous visit.

[†]Prior to study vaccination.

⁻Review/confirm information or activity in subjects previously consented and screened/enrolled. This includes review of the pregnant woman's medical chart to obtain information about this pregnancy that may be relevant to the conduct of this study.

[^]Review results of all clinical screening or safety laboratory evaluations.

[@]Complete medical history, medication use, and vaccination history by medical record review and interview of subjects to be obtained prior to study vaccination (screening or Day 1) and interim medical history, medication use, and vaccination history by interview of subjects to be obtained at follow-up visits.

[†]All current medications and vaccinations taken within 90 days prior to vaccination will be reviewed, but only those taken within 30 days prior to vaccination and through discharge after delivery for pregnant women will be recorded in Advantage eClinical.

[%]Subjects must not eat or drink anything hot or cold, or smoke within 10 minutes prior to taking oral temperature.

[/]If AE or SAE occurs post-vaccination.

{ Targeted physical examination, if indicated based on review of complete or interim medical history. An examination performed by a pregnant woman's own obstetrical clinician may also provide data when a targeted exam is called for. An exam should be performed for both the mother and infant if indicated for pregnant women on and after birth.

^{\$}Vital signs assessed on Day 1 (Visit 01) prior to the study vaccination will be considered as baseline and used to determine eligibility. For the birth visit, vital signs recorded for the mother as part of her delivery record may be used in lieu of study personnel performing vital sign measurements.

[#]A physical examination performed as part of routine antenatal care or a study-specific brief exam may be used.

[!]If within 30 days post vaccination.

^{*} If within 8 days post vaccination.

^{*}SAEs and new-chronic onset medical conditions only after Day 31 or delivery, whichever occurs earlier.

⁺Only medically attended AEs will be recorded.

[¶] The first colostrum collection may occur within the first 4 days of life of the infant.

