#### 9.1.2. Prior and Concomitant Medications

During screening, medications used up to 90 days prior to signing informed consent will be solicited. Any medications used within 30 days prior to vaccination through discharge after delivery for pregnant women and the day of life 180 visit for infants (or early termination if prior) will be recorded in the eCRFs.

Summaries of medications that were started prior to dosing and continuing at the time of dosing will be presented by WHO Anatomical Therapeutic Classification (ATC) Levels 1 and 2 and treatment group ([Table 73](#) and [Table 74](#)).

Individual subject listings will be presented for all concomitant medications ([Listing 17](#)).

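### The delivery-visit instruction limits recording of maternal medications and vaccinations to births within 30 days of vaccination, contradicting Protocol 6.6 and the SAP, which run to discharge after delivery

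*Protocol*

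**What the plan says.** One group of passages records maternal products up to discharge after delivery:

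- Protocol 6.6 says so for the data collection form ("until discharge after delivery for pregnant women") and again for the eCRF ("limited to those taken within 30 days prior to study vaccination through discharge after delivery for pregnant women").
- Protocol 8.1 defines the medication history by reference to the intervals in 6.6.
- The medication footnote in Appendix A, repeated under SAP Table 2, says "only those taken within 30 days prior to vaccination and through discharge after delivery for pregnant women will be recorded in Advantage eClinical".
- SAP 4.4.7 repeats 6.6. SAP 9.1.2 has "Any medications used within 30 days prior to vaccination through discharge after delivery for pregnant women"; that sentence names medications only, not vaccinations.

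A second group stops at 30 days:

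- The V05 procedure in Protocol 7.4.2.2.1 says "concomitant medications/vaccinations if less than 30 days post vaccination".
- In SAP Table 2 the V05 cells for Concomitant Medications and for Vaccination History carry the '!' mark, defined as "If within 30 days post vaccination". The same footnote stands in Appendix A, but the superscripts on the Appendix A cells cannot be read with certainty in the text available.

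The text for the postpartum visits V06 to V08 asks for infant concomitant medications and does not mention the mother's.

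**The concern.** V05 is the only scheduled maternal visit between Day 31 and discharge. If its instruction is taken literally, maternal products taken after the Day 31 visit are not asked for at the one contact where they could be collected routinely. For most women that is the later part of pregnancy and the delivery admission.

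Two things would suffer:

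- **Medication summaries.** SAP 9.8 summarises medication use during the study in Table 73 and lists it in Listing 17. Both would be short of their stated period, with nothing in the output to show it, and the shortfall could differ according to which instruction staff followed.
- **Support for pregnancy-related adverse events.** These are a primary safety outcome. Several grades in Protocol Table 8 turn on treatment given: days of parenteral antibiotics for endometritis, start of medical therapy for gestational diabetes, transfusion for haemorrhage. Listing 17 has a column linking each medication to an adverse event, and 6.6 uses a new non-routine medication as a prompt to look for a new diagnosis. Both uses depend on the medication being recorded.

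**Working it through.** The plan gives no figure to reproduce. The check is date arithmetic on gestational age, in days.

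**Inputs**

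- Vaccination window, Protocol 6.3: "the dose will be administered between 14 0/7 weeks gestation and 26 6/7 weeks gestation". That is 14 × 7 = 98 days to 26 × 7 + 6 = 188 days.
- V05 condition: less than 30 days after vaccination, so at most 29 days.
- Day 31 visit (V04): vaccination + 30 days, with a window of ±4 days. V04 records all new concomitant medications and vaccinations.
- Births at 37 0/7 weeks (259 days) and 40 0/7 weeks (280 days), taken as illustrations.

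**Which births meet the V05 condition**

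Latest qualifying birth = gestational age at vaccination + 29.

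- Vaccinated at 26 6/7: 188 + 29 = 217 days = 31 0/7 weeks.
- Vaccinated at 14 0/7: 98 + 29 = 127 days = 18 1/7 weeks.

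No birth after 31 0/7 weeks qualifies, whenever in the window the woman was vaccinated. Reading the footnote as allowing day 30 itself moves this by one day.

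**Days between the Day 31 visit and birth**

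The Day 31 visit falls at 188 + 30 = 218 days (latest vaccination) or 98 + 30 = 128 days (earliest).

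| Birth at | Vaccinated 26 6/7 | Vaccinated 14 0/7 |
|---|---|---|
| 37 0/7 | 259 − 218 = 41 | 259 − 128 = 131 |
| 40 0/7 | 280 − 218 = 62 | 280 − 128 = 152 |

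As a share of the time from vaccination to birth:

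- Birth at 37 0/7: 41/71 = 58% to 131/161 = 81%.
- Birth at 40 0/7: 62/92 = 67% to 152/182 = 84%.

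With the ±4-day window the overall range becomes 41 − 4 = 37 to 152 + 4 = 156 days. The Protocol Summary itself expects 3 to 7 months of pregnancy after vaccination, which fits.

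**How many women could meet the condition**

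The documents give no distribution of gestational age at birth, so this is an assumption. Take a normal distribution with mean 38 to 40 weeks and SD 1.5 to 3 weeks. At most 0.09% of women would qualify if vaccination were spread evenly over the window, and at most 1.0% (about 2 of 200) if all were vaccinated at 26 6/7. More crudely, if 1% to 5% of births came by 31 0/7 weeks, no more than 2 to 10 of 200 women could qualify.

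**What the V05 line was probably meant to limit**

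Protocol 9.3 ends non-serious adverse events at Day 31 or delivery, whichever is first, so a 30-day condition belongs to them. Protocol 7.6 and 7.7 tie medications to their own collection period, separately from adverse events. The V05 wording looks like the adverse-event window carried over to medications. That is an inference; the contradiction does not depend on it.

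**The case against.** The strongest reply is that 6.6 governs. It is the section on this topic, it states the period twice, 8.1 points to it, and the SAP follows it. A site that works from 6.6 records everything. Protocol 7.4 also allows study staff to review the woman's chart at any time. This stands to a degree: loss is conditional on staff following the visit list. But chart review is optional, and the visit procedures and schedule are what staff work from.

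The V05 sentence also has unbalanced parentheses, so the reach of the 30-day condition is uncertain. That is fair, but the condition directly follows the medications, and the '!' on the two V05 cells in SAP Table 2 supports the restrictive reading. On the same table, the V06 to V08 medication cells carry a '~' symbol that has more than one footnote, one of which extends procedures to both mother and infant. A maternal catch-up after delivery can therefore be neither confirmed nor excluded from the table; the visit text names only the infant.

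A reader might infer more than this, and the documents do not support it:

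- **That the data are certain to be lost in nearly every woman.** The V05 condition excludes nearly every woman, but loss follows only where V05 is preferred to 6.6.
- **That the primary PT result is biased.** The infant per-protocol set for the primary analysis requires only a perinatal blood sample, the test is an unadjusted t-test on log concentrations, and allocation is randomised and blinded. Maternal medications enter neither the set nor the test.
- **That per-protocol exclusions would be missed.** The named maternal windows after vaccination (live vaccine 30 days, inactivated vaccine 14 days, immunosuppression 30 days) end at about the Day 31 visit, which records these products. The blood-product criterion covers only the 90 days before vaccination.

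**Conclusion.** The inconsistency is real and should be corrected. The V05 instruction and its schedule mark contradict Protocol 6.6, the schedule's own medication footnote and the SAP. Every birth after about 31 0/7 weeks falls outside the V05 condition; this follows from the vaccination window alone and needs no assumption.

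The size of the gap, 41 to 152 days for births at 37 to 40 weeks, assumes a Day 31 visit held on its nominal day, a site that follows the visit list, and no maternal catch-up after delivery. The consequence is that Table 73, Listing 17 and the medication support for pregnancy-related adverse events may be incomplete and inconsistent with their stated period. It does not extend to the validity of the primary immunogenicity comparison or to the named per-protocol exclusions.

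**What to change.** 1. In Protocol 7.4.2.2.1, remove the 30-day limit from concomitant medications and vaccinations, and repair the parentheses so that the limit applies only to non-serious adverse events.
2. Remove the '!' mark from the V05 Concomitant Medications and Vaccination History cells in SAP Table 2, and from the same cells in Appendix A where it appears.
3. State that V05 records maternal medications and vaccinations since the previous visit and up to discharge, as 6.6 already requires.
4. Leave the adverse-event window as it is.

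This closes the 41 to 152 day gap. It adds no new category of data: blood products, for example, are not named in 6.6 or SAP 9.1.2, and adding them would be a separate decision. The cost is the text corrections and a few more minutes of interview or chart review at a visit that already takes an interim history.
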